
Subjects who were not enrolled in the MTD cohort can increase to the MTD after week 16 if the participant still meets the eligibility criteria. Responding patients will be able to continue treatment until marketing approval of ruxolitinib for CMML. **Duration of** Subjects will be followed as per calendar on treatment for 17 weeks. After 17 weeks, subjects who continue on study will be followed monthly. Off study data on AML transformation and Follow-Up overall survival will be updated every 6 months or until death, whichever occurs first. Subjects removed from the study for unacceptable adverse events will be followed until resolution or stabilization of the adverse event. Criteria for Removal from Study Study drug treatment can continue for subjects receiving clinical benefit, unless; one or more withdrawal criteria are met, or at the subject's discretion, or if the study is terminated, or until the marketing approval for CMML *Subject Completion A subject will be considered to have completed the study if the subject meets at least 1 of the following criteria: - The subject has completed 16 weeks of treatment with study medication with no improvement. - The subject died during the study. - The subject withdrew from study including subjects who experience a DLT. - The subject experienced an AE that lead to withdrawal from the study. *Subject Withdrawal from Study A subject may voluntarily withdraw from study medication or withdraw consent from the study at any time. The investigator may also, at his or her discretion, discontinue a subject from participating in the study at any time. The investigator will record the date and the reason for subject withdrawal from the study. *Subject Withdrawal from Study Medication If the subject is permanently withdrawn from treatment with study medication, but does not withdraw consent, the investigator must make every effort to have the subject complete all withdrawal assessments at the time of withdrawal, and complete all scheduled follow-up visits. Treatment with study medication must be discontinued if (Withdrawal Criteria): • No clinical benefit has been attained after 16 weeks of treatment. • Evidence of Disease progression according to IWG 2006 criteria. a subject experiences a DLT. • a subject becomes pregnant. • a subject is significantly non-compliant with the requirements of the protocol; • a subject has an adverse experience that would, in the investigator's judgment, make continued participation in the study an unacceptable risk See calendar page 36 Follow up on study **Statistics Study Design:** This study will use a dose escalation, "rolling 6" design in Phase 1. Subjects will be allocated to starting doses of 10 mg/d to 40mg/d (divided in two equal doses) escalated by 10 mg/day for each cohort according to the predetermined algorithm outlined below in Table 1 (section 6.4). Each cohort will include 6 subjects. After testing the treatment dose on 10 patients in the first stage, the trial will be terminated if 1 or fewer desired respond. If the trial goes on to the second stage, a total of 29 patients will be studied. If the total number responding is less than or equal to 5, the drug is rejected. *Sample Size/Accrual Rate

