6.6 Prohibited Medications

Subjects must abstain from using prohibited prescription or non-prescription drugs within 7 days or 5 half-lives (whichever is longer) prior to the first dose of study medication and until completion of follow-up procedures (Exclusion Criteria). The following medications are prohibited during the study:

- Any prior or concomitant use of another JAK inhibitor.
- Any investigational medication other than the study drugs.
- Use of the potent inducers of CYP3A4, rifampin and St John's Wart, is not permitted at any time during participation in the study.
- The GM-CSF growth factor receptor agonists must not be used. Preclinical evidence suggest that it is important for CMML proliferation and survival and it is directly upstream for JAK2, the target of ruxolitinib. GM-CSF must not have been used for at least 28 days prior to receiving the first dose of study drug.

7 **Duration of Therapy**

Subjects will be treated for a total of 16 weeks. For subjects responding at week 16, treatment may continue until one of the following criteria applies:

- 7.1 Dose-limiting toxicity is reached,
- 7.2 Inter-current illness that prevents further administration of treatment,
- 7.3 Unacceptable adverse event(s),
- 7.4 Patient decides to withdraw from the study, or
- 7.5 General or specific changes in the patient's condition render the patient unacceptable for further treatment in the judgment of the investigator.
- 7.6 Evidence of disease progression by the IWG 2006 criteria.

Subjects who wish not to continue treatment will complete their end of study visit at week 17. Subjects who were not enrolled in the MTD cohort can increase to the MTD after week 17 if the participant still meets the eligibility criteria. Responding patients will be able to continue until marketing approval of ruxolitinib for CMML.

8 Duration of Follow-Up

Subjects will be followed as per calendar on treatment for 17 weeks. After 17 weeks patient who continue on study will be followed monthly. Off study data on AML transformation and overall survival will be updated every 6 month or until death, whichever occurs first. Subjects removed from study for unacceptable adverse events will be followed until resolution or stabilization of the adverse event.

9 Criteria for Removal from Study

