9.1 Subject Completion

A subject will be considered to have completed the study if the subject meets at least 1 of the following criteria:

- 9.1.1 The subject has completed 16 weeks of treatment with study medication with no improvement.
- 9.1.2 The subject died during the study.
 - 9.1.3 The subject withdrew from study including subjects who experience a DLT.
- 9.1.4 The subject experienced an AE that lead to withdrawal from the study.

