9.3 Subject Withdrawal from Study Medication

If the subject is permanently withdrawn from treatment with study medication, but does not withdraw consent, the investigator must make every effort to have the subject complete all withdrawal assessments at the time of withdrawal, and complete all scheduled follow-up visits. Treatment with study medication must be discontinued if:

- The subject withdraws consent.
- Further participation would be injurious to the subject's health or well-being in the Investigator's medical judgment.

- The study is terminated.
- Marketing approval of CMML
- The subject becomes pregnant
- The subjects exhibits leukemic transformation (as evidenced by bone marrow blast counts of at least 20%, or peripheral blast counts of at least 20% lasting at least 8 weeks.
- No clinical benefit has been attained after 16 weeks of treatment.
- Evidence of Disease progression according to IWG 2006 criteria.
- a subject experiences a DLT.
- a subject is significantly non-compliant with the requirements of the protocol.
- a subject has an adverse experience that would, in the investigator's judgment, make continued participation in the study an unacceptable risk.

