10 DOSING DELAYS/MODIFICATIONS

All subjects enrolled in the phase 1 portion will start treatment on the assigned dose per cohort based on the dose escalation algorithm provided. No dose delays or modifications are allowed during this period. All subjects enrolled in the phase 2 portion may have the following dose delays/modifications once the MTD has been defined.

Ruxolitinib may be held by the Investigator at any time if there is concern about subject safety. Dosing must be halted immediately if either of the following occurs:

- Platelet counts fall below 10,000/μL and/or a life-threatening bleeding event
- Febrile neutropenia

Dosing may be reinstated following dose interruption using the re-start schema detailed in below.

10.1 Dose Adjustments.

In order to provide sufficient data to make the dose adjustment decisions, it is recommended that hematology parameters be obtained weekly and at least two times weekly for platelet count $< 25,000/\mu L$ or ANC $< 500/\mu L$. In the event that any subject permanently discontinues the study drug, regardless of reason, reasonable efforts should be made to have the subject return for an early termination visit. If the drug discontinuation is being contemplated for a reason other than low platelet count or

low ANC, the use of a tapering strategy should be considered (see below). The date the subject discontinued the study drug and the specific reason for discontinuation will be recorded in the eCRF; eg, reasons such as discontinued due to inadequate efficacy or withdrawn due to adverse event. This information will be used to summarize the reasons for study discontinuation. Efforts will be made to follow subjects who discontinue from the study in order to determine overall survival and leukemia free survival. Investigators will contact subjects every 6 months to determine if subjects have undergone leukemic transformation, or death, and for the latter, the cause of death.

10.2 Dose Adjustments in Ruxolitinib Tablets for Safety.

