Dose adjustments apply to the phase 2 portion of this study. There are no dose adjustments allowed during phase 1. Dosing must be held if platelet counts decline below 10,000/μL or if a life-threatening bleed occurs with a platelet count below 20,000/μL. Doses must be decreased for platelet count values that decline greater than 50% of baseline and are greater than 25,000/μL to 75% of the defined MTD. Doses must be decreased for platelet count values that decline greater than 50% of baseline and are below 25,000/μL to 50% of the defined MTD. The dosing scheduled should be maintained at BID dosing to assure appropriate pharmacokinetics. Dose reductions should be executed by decreasing the individual dose and not the frequency of administration. In order to provide sufficient data to make the dose adjustment decisions, it is recommended that hematology parameters be obtained as defined in section 10.1. Dosing may be restarted or increased following recovery of platelet counts to acceptable levels. The following is the recommended dose restart/increase strategy:

In subjects whom drug was held, ruxolitinib may be restarted at 50% of the MTD after platelet count has improved to pre-ruxolitinib baseline levels and/or febrile neutropenia has resolved for at least 2 weeks. In subjects whom drug dose was decreased, ruxolitinib may be increased to the previous dose (MTD) after platelet count has improved to pre-ruxolitinib baseline levels and/or febrile neutropenia has resolved for at least 2 weeks. If criteria is met for discontinuation/dose modification then ruxolitinib must be discontinued with no potential for restart. The objective for

restarting or escalating after a reduction for safety is to find the highest safe dose of ruxolitinib for each subject, with increases in dose generally not more than in increments of 5 mg BID and not more often than every 2 weeks. Subjects who were not enrolled in the MTD cohort can increase to the MTD after week 17 if the participant still meets the eligibility criteria. Non hematological toxicity dose adjustment criteria

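### In phase 2, a platelet fall of more than 50% to a count of 10,000 to under 25,000/µL requires both half the MTD (10.2) and discontinuation as a DLT (9.3)

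*Combined protocol and SAP*

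**What the plan says.** **Dose modification.** Section 10 bars modifications in phase 1 and then says "All subjects enrolled in the phase 2 portion may have the following dose delays/modifications once the MTD has been defined". Section 10.2 repeats that it applies to phase 2. For severe thrombocytopenia it states "Doses must be decreased for platelet count values that decline greater than 50% of baseline and are below" 25,000/µL, to 50% of the MTD, and allows a later return to the MTD. Below 10,000/µL dosing must be held; after a hold, "ruxolitinib may be restarted at 50% of the MTD after platelet count has improved to pre-ruxolitinib baseline levels". It then adds "If criteria is met for discontinuation/dose modification then ruxolitinib must be discontinued with no potential for restart".

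**DLT.** Section 6.2 and the synopsis make any grade 4 hematologic toxicity a DLT. They give a trial-specific definition of grade 4 thrombocytopenia: in the synopsis, a fall of more than 50% to below 25,000/µL; in 6.2, at least 50% to 25,000/µL or lower. Section 6.2 restricts only the escalation decision to the first 8 weeks and has DLTs evaluated in every cycle.

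**Stopping.** Section 9.3 lists the conditions under which drug must be discontinued, among them that "a subject experiences a DLT". The synopsis withdrawal criteria carry the same item directly after progression: "Evidence of Disease progression according to IWG 2006 criteria. a subject experiences a DLT". Section 9.1.3 counts DLT subjects as withdrawn: "The subject withdrew from study including subjects who experience a DLT". Section 7.1 ends continued treatment after week 16 when "Dose-limiting toxicity is reached", and the continuation-phase text in Section 13 allows continuation only while there is no DLT. None of these is limited to phase 1.

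**The concern.** The count that triggers the half-dose rule is the count that defines the DLT. One section then orders continued treatment at a lower dose, and another orders discontinuation. Two investigators following the protocol could treat the same patient with severe thrombocytopenia in opposite ways, and either could be charged with a deviation.

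There is also a smaller analysis consequence. Section 15.5 defines evaluable subjects as those with at least 8 weeks of therapy and the first on-treatment marrow. A subject stopped before week 8 cannot meet that definition; one kept on at half dose may.

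**Working it through.** The plan gives no figure on this point, so the check sets the trigger regions side by side. Let *b* be the baseline platelet count and *c* the current count, in thousands per µL.

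Inputs:
- Entry limit: *b* ≥ 35 (4.2.1.1).
- 50% reduction (10.2): *c* < 0.5*b* and *c* < 25, with *c* ≥ 10 so that the hold for low counts does not apply.
- Hold (10.2): *c* < 10. A life-threatening bleed with *c* < 20 also calls for a hold and is set aside here.
- Platelet DLT: *c* < 0.5*b* and *c* < 25 (synopsis), or *c* ≤ 0.5*b* and *c* ≤ 25 (6.2).

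**Reduction branch.** The region is 10 ≤ *c* < min(25, 0.5*b*).

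| Baseline | 0.5*b* | Counts requiring 50% of MTD | Also a DLT? |
|---|---|---|---|
| 35 | 17.5 | 10 to <17.5 | all |
| 40 | 20 | 10 to <20 | all |
| 45 | 22.5 | 10 to <22.5 | all |
| 50 or more | 25 or more | 10 to <25 | all |

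The two cut-offs equal those of the synopsis DLT and lie inside the 6.2 definition, so the small wording difference between those definitions does not matter. Example: 60 to 20 is a fall of (60 − 20)/60 = 66.7%. Section 10.2 requires half the MTD; 9.3 requires a stop.

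**Hold branch.** With *b* = 35, any count below 10 is a fall of more than 1 − 10/35 = 71.4%. With *b* = 50 it is more than 80%, and with *b* = 100 more than 90%. So if the baseline is at least the entry limit, every such count is a DLT. Example: 35 to 9 is a fall of 26/35 = 74.3%. Here the hold is mandatory and the restart optional. Holding and then discontinuing satisfies both sections; using the restart breaches 9.3.

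**Where there is no conflict.** The step to 75% of the MTD applies above 25, so it is outside the platelet DLT. A fall of less than half is also outside: 40 to 22 is 18/40 = 45%, and neither the reduction rule nor the platelet DLT applies.

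**Does any text give precedence?** No section ranks 10.2 against 9.3. The sentence "If criteria is met for discontinuation/dose modification then ruxolitinib must be discontinued with no potential for restart" does not help. Read literally, it cancels the reduction and restart scheme just set out. If a second event is meant, it does not say so, whereas 10.4 does say so for hepatic impairment.

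**Design figures.** The Simon rule (1/10, 5/29; 10% versus 30%) uses none of these inputs. Exact binomial sums give early termination 0.736, type I error 0.047 and type II error 0.195, against the stated 0.74, 0.05 and 0.19.

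**The case against.** The best defence is that the specific rule prevails over the general one. Section 10.2 is written for phase 2 and for platelets, while the DLT item in 9.3 is a generic bullet. The synopsis explains that modifications are barred in phase 1 because they would disturb the primary endpoint, and then allows them in phase 2. Section 6.2 itself closes by sending management and dose modification of these events to another section. It names Section 11, which covers reporting, so Section 10 was probably meant. This makes it likely that 10.2 was intended to govern phase 2. It does not resolve the text: no passage says so, 9.3 is mandatory and carries no phase limit, and 6.2, 7.1, 9.1.3 and the continuation text carry DLT evaluation or stopping beyond phase 1.

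A reader might argue instead that only drug-related falls count, since the MTD definition in 3.1.1 refers to drug-related DLTs. But 6.2 says the count rule is itself the means of separating drug effect from disease effect, and a drug-related fall that meets it is still in conflict.

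Three stronger readings are tempting and are not supported:
- That the rules below 10,000/µL are equally irreconcilable. They are not: only the hold is mandatory.
- That every count below 10,000/µL is a DLT, so a restart after a platelet hold could never be used under 9.3. This depends on baseline, and the documents do not say that the DLT baseline is the screening count. Screening may be up to 4 weeks before treatment, a week 1 blood count is scheduled, and Section 14 provides for baselines under 20 × 10⁹/L. From 18,000 to 9,500/µL is a fall of 8.5/18 = 47%: a hold, no platelet DLT, and restart permitted.
- That phase 2 power is reduced. The documents give no rate for this event and no link between it and response, so any power loss would be invented.

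**Conclusion.** The contradiction stands. In phase 2, for a platelet fall of more than 50% to a count of 10,000 to under 25,000/µL, the half-dose rule and the DLT stop are both mandatory and cannot both be followed. Below 10,000/µL the conflict is narrower, between a permitted restart and a required discontinuation. It arises whenever the count is also a DLT, which is always so if baseline is at least 35,000/µL.

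The consequence is for patient dosing and safety. The number of subjects affected cannot be estimated from the documents. The Simon design is unaffected, and the ITT analysis includes the subject either way. Entry to the evaluable analysis may be affected, but 15.5 also requires the marrow and does not say whether time on hold counts as therapy. This should be corrected, but it does not threaten the primary analysis.

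**What to change.** State which rule prevails.

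1. If Section 10 is meant to govern phase 2, say so in 9.3, 9.1.3, 7.1, the synopsis withdrawal and duration criteria, and the continuation-phase text. In phase 2, toxicities for which Section 10 gives a hold, reduction or restart rule (platelets, febrile neutropenia, hepatic dysfunction) are managed under Section 10. The DLT stop applies in phase 1 and to phase 2 DLTs that Section 10 does not cover. An exemption for platelets alone would leave the same clash where febrile neutropenia or hepatic dysfunction reaches DLT grade.
2. Correct the cross-reference at the end of 6.2 from Section 11 to Section 10.
3. Reword the last-quoted sentence of 10.2 to say when drug stops for good, for example at a second event as in 10.4. That is a clinical choice for the investigator; the documents do not state it for platelets.

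If the DLT stop is intended in phase 2, delete instead the 50% reduction branch of 10.2 and the restart after a platelet DLT.

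Either route is a change of protocol wording only. It adds no visits, tests or analyses and leaves the response criteria and sample size alone.

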6 TREATMENT PLAN

6.1 Ruxolitinib administration

Subjects will not take the morning dose of ruxolitinib at the first regularly scheduled visit. Drug will be administered in the clinic in order to obtain adequate biomarker assessment. On all other days corresponding to study visits, subjects will take the morning dose of study drug prior to the visit, and will note on the subject reminder card the time that medications were taken. Reported adverse events and potential risks are described in Section 11. Appropriate dose modifications for ruxolitinib are described in Section 10. No investigational or commercial agents or therapies other than those described below may be administered with the intent to treat the patient's CMML.

6.1.1 Ruxolitinib will be supplied by INCYTE as tablets that will be self-administered BID orally, with or without food approximately 12 hours apart (morning and night).

6.1.2 The dosage strength is 5 mg/tablet Ruxolitinib phosphate (free base equivalent). Administration instructions will be provided at Study Visits. The administration instructions will state that medication is "For Investigational Use Only". Ruxolitinib 5 mg tablets are packaged as 60 count in high-density polyethylene (HDPE) bottles. The bottles will include labeling "New Drug - Limited by Federal (USA) Law to Investigational Use. The bottles of tablets should be stored at room temperature, 15°C to 30°C (59°F to 86°F). Dose escalation guidelines are detailed below in section 6.5. In phase II of the study, a maximum of 29 subjects will be treated at the MTD identified in phase I.

6.2 **Definition of Dose-Limiting Toxicity**

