10.4 Dose Reductions for Hepatic Impairment

Hepatic impairment will be classified by the NCI Organ Dysfunction Working Group criteria. Any hepatic dysfunction classified as moderate or severe will require the treating physician to hold study drug until two week after hepatic dysfunction can be classified as mild or normal by NCI criteria. Ruxolitinib may be restarted at 50% of the MTD. If moderate or severe hepatic impairment occur a second time in the same subject, ruxolitinib will be discontinued.

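### In section 10.2 (phase 2) the permanent-stop sentence omits a repeat-occurrence condition and, read literally, cancels the return-to-MTD and restart rules beside it

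*Combined protocol and SAP*

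**What the plan says.** Section 10 introduces the phase 2 rules with: "All subjects enrolled in the phase 2 portion may have the following dose delays/modifications once the MTD has been defined". Section 10.2 then sets the platelet rules. For the upper tier it says "Doses must be decreased for platelet count values that decline greater than 50% of baseline and are greater than 25,000" per microlitre, and the reduced dose is 75% of the MTD. A fall of more than half to a count below 25,000/uL means 50% of the MTD. A count below 10,000/uL means a hold. The lead-in to section 10 also requires a halt for febrile neutropenia.

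On recovery, held subjects may restart at 50% of the MTD. For reduced subjects, "ruxolitinib may be increased to the previous dose (MTD) after platelet count has improved to pre-ruxolitinib baseline levels". The sentence directly after these two rules is: "If criteria is met for discontinuation/dose modification then ruxolitinib must be discontinued with no potential for restart". The one after that explains the aim of restarting, or escalating after a reduction, as finding each subject's highest safe dose.

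Section 10.4 has a similar hold, restart and stop sequence, but states when the stop applies: "If moderate or severe hepatic impairment occur a second time in the same subject, ruxolitinib will be discontinued". Section 9.3 separately requires treatment to stop on any DLT.

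**The concern.** The stop sentence in 10.2 is mandatory and names dose-modification criteria as a trigger. It does not say that the criteria must be met again. Taken at its word, the platelet fall that calls for a reduction also ends treatment for good. The permissive rules just before it, return to the MTD and restart at half the MTD, would then never operate.

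What is at stake is who stays on drug in phase 2. Under the literal reading, a subject with a first platelet fall that is not a DLT loses treatment permanently. Under the likely intended reading, the same subject is reduced, recovers and returns to the MTD. Section 17.6 expects subjects at the lead center and at other institutions, so more than one team may have to interpret the sentence.

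**Working it through.** The plan states no figure on this point, so there is none to reproduce. The check sets the rules side by side and classifies each trigger against the DLT definition.

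**1. Does the stop sentence reach a platelet reduction?** The lead-in to section 10 uses the label delays/modifications for the changes that follow, so a 10.2 reduction is a dose modification. Section 9.3 lists only reasons to stop and contains no dose-modification criteria. It therefore cannot be the sole referent.

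**2. What happens to a reduced subject, read literally?** Reduction is required; return to the MTD is allowed on recovery; permanent discontinuation is required once modification criteria are met. The first and third steps share one trigger, so the second can never be reached.

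**3. Which triggers does 9.3 already stop?** Let B be the baseline platelet count and P the on-treatment count. Inputs:
- Tier limits, from 10.2.
- DLT platelet criterion, from 6.2: a fall of at least 50% and a count of 25,000/uL or lower. The synopsis words both limits as strict inequalities, which does not change the results below.
- Platelet floor of 35,000/uL, from 4.2.1.1. I assume that B is at or above this floor.

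| Trigger | Condition | Consequence | Platelet DLT? |
|---|---|---|---|
| 75% tier | P < 0.5B and P > 25,000 | B > 25,000/0.5 = 50,000 | No: P is above the DLT level |
| 50% tier | P < 0.5B and P < 25,000 | Both DLT conditions met | Yes: 9.3 applies |
| Platelet hold | P < 10,000 and B ≥ 35,000 | Fall > 1 − 10,000/35,000 = 71.4% | Yes: 9.3 applies |

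The 75% tier is thus outside the platelet DLT throughout, and it is empty for baselines from 35,000 to 50,000/uL. There, no 9.3 platelet stop intervenes and the two 10.2 rules conflict directly. In the other two rows 9.3 already ends treatment, so the stop sentence adds no separate conflict.

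**4. Example.** Baseline 150,000/uL, on treatment 70,000/uL. The fall is 1 − 70/150 = 53.3%, and the count is 70,000/25,000 = 2.8 times the DLT level. The reduction and return rules give 75% of the MTD and then the full MTD on recovery. The literal stop sentence gives permanent discontinuation at this first event.

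**5. Febrile neutropenia.** The section 10 lead-in requires a halt, and 10.2 allows restart at 50% of the MTD once the event has been resolved for at least two weeks. Section 6.2 defines grade 4 neutropenia by a fall of at least 50% and a count below 500/uL, and counts non-hematologic toxicity of grade 3 or above as a DLT. It does not say where febrile neutropenia belongs. If the event is a DLT, 9.3 stops treatment. If it is not, the literal sentence conflicts with the restart rule here too.

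**The case against.** The strongest reply is that context settles the meaning. The lead-in to section 10 allows dosing to be reinstated, 10.2 gives separate recovery rules for held and reduced subjects, and the sentence after the disputed one presupposes escalation after a reduction. A first-event stop would make all of this pointless, and 10.4 shows the drafters' pattern. This stands: a repeat-event rule is the likely intent, and a reader might wrongly infer a deliberate first-event stop. It lowers the weight of the point without supplying the missing condition. The text still does not say which event must recur.

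It is also fair that subjects would not be unprotected if the sentence were set aside. The investigator may hold drug at any time (section 10) and must stop it when continuing is judged an unacceptable risk (9.3). Different handling across institutions is a possibility, not a finding. Section 17.6 provides biweekly review by the investigator and study team and monthly committee review, both covering adverse events and protocol violations.

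Finally, 10.2 ends on a heading about non-hematological dose adjustment with nothing beneath it, perhaps lost in reading the PDF. The sentence might refer partly to that text. The point therefore rests only on the platelet and febrile-neutropenia rules that are present.

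**Conclusion.** The point holds as a minor wording correction to an operative dosing rule. As written, 10.2 turns a first reduction into a permanent stop and cancels its own recovery rules. The conflict is clear at the 75% tier, which requires a baseline above 50,000/uL, and possible for febrile-neutropenia holds. It should not be extended to the 50% tier or to the hold below 10,000/uL, because 9.3 governs both.

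A reader might go further and infer that the phase 2 response rate or the Simon boundaries are compromised. The documents do not support that. They give no frequency for 75%-tier falls, so no number of affected subjects can be stated. Section 15.5 also keeps every treated subject in the main efficacy analysis whatever the duration of treatment.

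The conclusion assumes that baseline counts respect the eligibility floor and that the dose-modification criteria in the stop sentence include the platelet reductions in the same section.

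**What to change.** Replace the sentence in 10.2 with:

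> If criteria for a hold or dose reduction are met a second time in the same subject, after restart or return to the previous dose, ruxolitinib must be permanently discontinued. A subject who worsens to a lower platelet tier while on a reduced dose is handled by that tier's rule, subject to the 9.3 DLT stop.

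The second sentence is needed because a subject can worsen before any restart or return to the previous dose.

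The sponsor should confirm one clinical decision: whether a second 75%-tier fall, which is not a platelet DLT, should end treatment. This matters because 9.3 already stops the 50% tier and the hold below 10,000/uL at the first event. Among the platelet rules, the new sentence would therefore act mainly on repeated 75%-tier falls. Stating in 6.2 whether febrile neutropenia is a DLT would close the remaining gap.

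The cost is two sentences in 10.2, that sponsor decision and one clarification in 6.2. Sample size, endpoints and analysis do not change.
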